1. PROTOCOL SUMMARY

1.1. Synopsis

A Phase 2, Multicenter, Randomized, Double-blind, Placebo-controlled Study with Deferred Active Treatment to Investigate the Efficacy, Safety, and Pharmacokinetics of JNJ-73763989 + Nucleos(t)ide Analog in Participants Co-infected with Hepatitis B and Hepatitis D Virus.

JNJ-73763989 (JNJ-3989) is a 2:1 molar mixture of 2 synthetic, double-stranded, N-acetylgalactosamine (GalNac) conjugated RNAi triggers (JNJ-73763976 and JNJ-73763924, respectively). RNAi is a naturally-occurring phenomenon by which short, double-stranded RNA oligonucleotides trigger a sequence-specific down modulation of gene expression. The RNAi triggers in JNJ-3989 are designed to target all hepatitis B virus (HBV) transcripts derived from covalently closed circular DNA (cccDNA) and integrated viral DNA. This is made possible by the fact that all HBV transcripts expressed from cccDNA, including the RNA transcript (pre-genomic ribonucleic acid [pgRNA]) that is used as a template for replication of HBV DNA, are terminated by the same polyadenylation site and share a common sequence region upstream of this site. One RNAi trigger (JNJ-73763924) in JNJ-3989 has its target within this common sequence region and thus has the potential to knock down expression of all viral proteins as well as the pgRNA expressed from cccDNA. The second RNAi trigger (JNJ-73763976), which targets the HBsAg encoding region, was designed to knock down expression of hepatitis B surface antigen (HBsAg) derived from integrated HBV DNA as well as all viral proteins derived from cccDNA with the exception of HBV x protein. Silencing viral RNA will reduce HBV DNA and viral proteins, including HBsAg. Since HBsAg is required for replication of hepatitis D virus (HDV), by allowing HDV to infect new cells, reducing HBsAg levels is anticipated to lead to inhibition of HDV replication.

Study intervention refers to JNJ-3989 or placebo and nucleos(t)ide analog (NA).

BENEFIT-RISK ASSESSMENT

Overall, JNJ-3989 administration was generally safe and well tolerated in the completed and ongoing studies, all of which except REEF-D are in CHB patients or healthy participants.

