At present there are no drugs approved for the treatment of chronic HDV infection. Pegylated interferon-alpha (PegIFN- α) is used in chronic HDV infection but is associated with significant toxicity and tolerability is poor in patients with decompensated cirrhosis. Treatment with PegIFN- α results in “sustained” virologic response rates (defined as undetectable HDV RNA levels 6 months after treatment) of 25%-30%.^{8,25} However, late virologic relapses after achieving “sustained” virologic response are common following treatment with PegIFN- α , and it is not known if HDV sustained clearance can be achieved in the setting of persistent HBsAg positivity.¹³ Although currently available HBV therapies are effective in suppressing HBV replication, the rate of HBsAg reduction and/or loss remains low.²² In the absence of HBsAg loss, HDV infection may persist. Therefore, therapies directly targeting HBsAg are expected to be of clinical benefit for hepatitis D treatment as well.²³

Suppression of HDV replication in combination with normal alanine aminotransferase (ALT) levels are the primary goals of HDV treatment since this has been shown to lead to improved clinical outcome.³ Consistent with this, the recent US Food and Drug Administration (FDA)’s draft guidance on the treatment of chronic HDV infection recommends the following as surrogate endpoint and primary endpoint for pivotal studies: a decline in virologic replication (eg, serum HDV RNA target not detected [TND] and/or HDV RNA decline of $>2 \log_{10}$ IU/mL from baseline) and an improvement in associated liver inflammation as evidenced by biochemical response (eg, normal ALT).²⁴

For the most comprehensive nonclinical and clinical information regarding JNJ-73763989 (JNJ-3989), refer to the latest version of the Investigator’s Brochure (IB) for JNJ-3989.

The term “study intervention” throughout the protocol, refers to JNJ-3989 or placebo, and nucleos(t)ide analog (NA).

The term “sponsor” used throughout this document refers to the entities listed in the Contact Information page(s), which will be provided as a separate document.

The term “participant” throughout the protocol refers to the common term “subject”.

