2.3.1.2. Potential Risks

All therapies have the potential to cause adverse experiences.

Patients with positive HDV RNA, HBV DNA, and positive HBsAg can always experience increases in liver transaminases which may indicate immune activation and may result in the reduction of viral parameters such as HDV RNA, HBV DNA, and/or HBsAg.

ALT elevations are considered an important potential risk for JNJ-3989. Two distinct patterns of ALT elevations have been observed in participants receiving JNJ-3989: a rapidly rising and resolving ALT elevation or a more sustained pattern of ALT elevation. During Parts 1 and 2 of this study, the latter has been observed in HBV/HDV co-infected participants, when receiving JNJ-3989 compared to placebo. In Part 2 of this study, the risk of confirmed ALT elevations was higher in participants with HBsAg levels >10,000 IU/mL at screening or baseline. A causal relationship between JNJ-3989 and ALT elevations is suspected. However, the mechanism for this type of confirmed ALT elevations seen with JNJ-3989 in treatment of patients with HBV/HDV co-infection is not yet understood.

The participants who are randomized to the deferred active treatment arm, could also be at increased risk for liver disease progression during the 52 weeks of placebo + NA treatment.

Participants who are HBV DNA suppressed are at risk for hepatitis B reactivation if NA treatment is discontinued. Reactivation of hepatitis B is defined by a sudden increase in HBV-DNA replication in participants with previously inactive CHB (resolved HBV infection or virologically suppressed). Although HBV reactivation can occur spontaneously, it can be triggered by immunosuppressive therapy (for autoimmune diseases or in the transplant setting), diseases associated with an immunocompromised state (cancer, human immunodeficiency virus infection), or the withdrawal of antiviral drugs.

Potential Risks for JNJ-3989

Reproductive Risks and Pregnancy

In the EFD studies, JNJ-3989 was not teratogenic in rats and rabbits. The fertility in male and female rats is not impacted with JNJ-3989 up to a dose of 180 mg/kg/week.

Based on the difference in metabolic pathways and in vitro data indicating absence of impact of JNJ-3989 on cytochrome P450 (CYP) enzymes and transporters, no clinically relevant interactions are anticipated between JNJ-3989 and oral contraceptives.

Potential Genotoxicity

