Note: For investigational COVID-19 vaccines administered within 6 months prior to screening, an exception will be made as long as the vaccine has been approved (or received emergency use authorization or conditional marketing authorization) at the time of screening.
-

Disallowed from 6 months prior to baseline until end of follow-up^a:

- Any systemically (eg, intravenously, intramuscularly, orally, subcutaneously) administered medication that directly or indirectly interferes with immune responses (eg, cyclosporine, interleukins, systemic corticosteroids exceeding 5 mg of prednisolone equivalent/day).
-

Disallowed from 1 month prior to screening until end of follow-up^a:

- Any medication that reduces renal function or competes for active tubular secretion (eg cimetidine, probenecid, quinidine).
-

Table 2: Disallowed Medication**Disallowed from screening until end of follow-up^a:**

- Biotin (>1 mg daily dose), either taken alone or as part of a multivitamin formulation.
Note: The use of other vitamins is allowed.
- Topical steroids (>7 days) under occlusive dressing.

^a Refer to Section 4.1 for the end of follow-up definition before and after Protocol Amendment 5.

Note: The list of disallowed medication is not exhaustive; for products falling in one of the categories and not mentioned by name, the sponsor should be contacted to determine whether the product can be allowed.

Note: Anticoagulants are to be used with caution. Aspirin and other antiplatelet aggregating agents are allowed. Further restrictions apply to participants undergoing optional liver biopsy procedures. Antiplatelet aggregating agents should be paused at least 9 days prior to liver biopsy procedures or according to local standard practice.

The sponsor must be notified in advance (or as soon as possible thereafter) of any instances in which prohibited therapies are administered.

The prescribing information for ETV, tenofovir disoproxil, and TAF should be consulted for any additional prohibited medication.

The sponsor must be notified in advance (or as soon as possible thereafter) of any instances in which prohibited therapies are administered.

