7. DISCONTINUATION OF STUDY INTERVENTION AND PARTICIPANT DISCONTINUATION/WITHDRAWAL

7.1. Discontinuation of Study Intervention

A participant's investigational study intervention (JNJ-3989/placebo) **must** be discontinued if any of the criteria listed below apply. In those cases, NA treatment should be continued.

- The participant withdraws consent to receive study intervention.
- The investigator believes that for safety reasons or tolerability reasons (eg, AE) it is in the best interest of the participant to discontinue study intervention.
- The participant becomes pregnant.
- The participant has a \geq grade 3 rash (see Section 10.5, Appendix 5, Rash Management) or allergic reaction (see Section 8.3.6.3).
- The participant has signs of hepatic decompensation (ie, clinical evidence of ascites, bleeding varices, or hepatic encephalopathy) or an increase in direct bilirubin $>1.5x$ ULN in combination with INR $\geq 1.5x$ ULN or albumin <3.0 g/dL. In this case treatment with JNJ-3989 should be discontinued and alternative treatment options (outside the study) should be considered in discussion with the sponsor.

- The participant has a confirmed \geq grade 3 estimated glomerular filtration rate (eGFR) abnormality and a drop from baseline of >10 mL/min/1.73 m², considered at least possibly related to JNJ-3989 that persists despite change of tenofovir disoproxil to ETV or TAF (if the patient was receiving tenofovir disoproxil). Change of NA treatment should be considered anytime, according to the prescribing information. (see Section 8.3.6.4).
- The participant has a confirmed QTcF prolongation (defined as a QTcF value of >500 ms, or an increase from baseline of >60 ms) at any given time point.
- The participant requires treatment with any of the disallowed medications listed in Section 6.7 and does not intend to discontinue treatment with the disallowed medication.
- The participant has confirmed HBV virologic breakthrough (ie, confirmed on-treatment HBV DNA increase by >1 log₁₀ IU/mL from nadir or confirmed on-treatment HBV DNA level >200 IU/mL in participants who had HBV DNA level $<$ LLOQ of the HBV DNA assay). In case of virologic breakthrough, changing the NA should be considered in consultation with the sponsor. Injection with JNJ-3989 will be stopped if the NA change does not result in a decrease in HBV DNA levels.
- The participant has ALT/AST elevations, as described in Section 8.3.6.1, Intervention-emergent ALT/AST Elevations.

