8.3.6.2. Rash

Participants should be informed that they should contact their doctor immediately when they notice any generalized skin reaction. This skin reaction should be evaluated in the clinic the same day (if possible) or the next day.

All rash events should be captured in the AE section of the CRF. A separate Rash page will be completed in case of a rash event.

Monitoring of the evolution of rash events will be performed as described in Table 3 in Section 10.5, Appendix 5: Rash Management.

When safety blood samples are drawn as per the rash management guidelines, these should be processed by the local laboratory. The following parameters will need to be tested: AST, ALT, sedimentation rate, complete blood cell count (including hemoglobin, hematocrit, red blood cell [RBC] count, white blood cell [WBC] count, differential count [neutrophils, lymphocytes, monocytes, eosinophils, and basophils], and platelet count), and creatinine. Relevant laboratory assessment values are to be shared with the sponsor (if applicable and local regulations allow) as per the “Instructions for Investigators for sharing of Digital Pictures and Local lab reports” and should be de-identified.

The participant may be treated symptomatically until the rash resolves. Oral antihistamines (eg, cetirizine, levocetirizine) and/or topical corticosteroids may provide symptomatic relief but effectiveness of these measures has not been established. If systemic corticosteroids exceeding 5 mg of prednisolone equivalent/day are required for treatment of rash, the study intervention needs to be permanently discontinued. If the rash is considered to be most likely due to concomitant illness or non-study drugs, standard management, including discontinuation of the likely causative agent, should be undertaken.

Injection Site Reactions

At the time points specified in the [Schedule of Activities](#) or at an unscheduled visit if needed, an evaluation of the injection site will be performed based on participant's description and/or physical examination. Evaluation will include at a minimum the time of occurrence, time of resolution and a description of the abnormality including its maximal diameter. For each ISR, information on pain, erythema, induration and pruritus should be obtained as specified in the DAIDS scale (see Section 10.9, Appendix 9: DAIDS Table).

All ISRs (including ISRs below grade 1) will need to be recorded in the special events section of the CRF.

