Continuation of Study Intervention

- Any issue with continuation and/or provision of study intervention should be discussed with the sponsor and should be well documented.
- Study intervention should be continued if, in the assessment of the investigator, it does not result in risk to the participant. If at any time a participant's safety is considered at risk due to study intervention, study intervention will be temporarily or permanently discontinued, while every effort should be made to maintain follow-up on study. The benefit of continuing study intervention should be assessed by the investigator for each individual participant, considering the potential impact of reduced direct clinical supervision on participant safety.

- If a participant develops a SARS-CoV-2 infection, the investigator should contact the sponsor to discuss plans for study intervention and follow-up. A decision to continue study intervention should be made by the investigator depending on symptoms and concomitant medication used for the treatment of COVID-19. Study intervention must be discontinued if prohibited medication is used.
- When a participant, for whom study intervention has been interrupted, recovers from suspected or confirmed SARS-CoV-2 infection or related disease and all AEs related to SARS-CoV-2 infection improve to Grade ≤ 1 , the investigator should discuss with the sponsor about resuming study intervention.

COVID-19 vaccination during the study:

Locally approved COVID-19 vaccines (including those that received emergency use authorization or conditional marketing authorization) are allowed throughout the study.

All COVID-19 vaccination-related data (eg, COVID-19 vaccination, AEs, AE management) should be appropriately captured in the CRF and source documents. Refer to the COVID-19 vaccine prescribing information for more details.

Study Visits and Assessments

- If possible, central laboratory testing as outlined in the [Schedule of Activities](#) is to be continued. If central laboratory tests cannot be performed, the use of a local laboratory is allowed for study evaluations. A copy of the local laboratory report should be reviewed by the investigator and filed with the source documents, along with reference ranges; to maintain treatment blinding, HBV/HDV RNA, HBsAg, HBeAg, HBcrAg, anti-HBs, and anti-HBe antibody tests during the study intervention phase cannot be done locally (unless instructed otherwise by the sponsor).

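### Two stopping sentences (8.3.6.2, steroids for rash; 10.10.1, prohibited medication) withdraw NA if the protocol's own definition is applied, against Section 7.1 or the general rule that NA continues

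*Protocol*

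**What the plan says.** The synopsis (Section 1.1) gives the definition: "Study intervention refers to JNJ-3989 or placebo and nucleos(t)ide analog (NA"). Section 2 repeats it and applies it to the whole document: the term, "throughout the protocol, refers to JNJ-3989 or placebo, and nucleos(t)ide analog (NA").

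Two stopping instructions use the term without naming a product. Section 8.3.6.2 (Rash): "If systemic corticosteroids exceeding 5 mg of prednisolone equivalent/day are required for treatment of rash, the study intervention needs to be permanently discontinued". Section 10.10.1 (COVID-19 guidance), in the item on participants who develop SARS-CoV-2 infection: "Study intervention must be discontinued if prohibited medication is used".

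Section 7.1 limits its mandatory stopping list to the investigational product, JNJ-3989/placebo, and says of NA: "In those cases, NA treatment should be continued". One criterion on that list is: "The participant requires treatment with any of the disallowed medications listed in Section 6.7 and does not intend to discontinue treatment" with that medication. Table 2 in Section 6.7 includes among the disallowed drugs "systemic corticosteroids exceeding 5 mg of prednisolone equivalent/day", the same threshold as in 8.3.6.2.

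Section 2.3.3 states as a risk measure that all participants stay on NA to their last visit. Its only exception, which predates Amendment 5, is for non-cirrhotic participants with confirmed HBsAg seroclearance, low ALT and unquantifiable HBV DNA. Sections 6.4 and 6.5.1 repeat continuation for all Part 2 participants.

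**The concern.** A site that applies the defined term as written would stop NA permanently when it starts systemic steroids for a rash, or would stop it when a prohibited drug is given during a COVID-19 illness. The protocol elsewhere wants NA kept, and it says why. Section 2.3.1.2 warns that HBV DNA-suppressed participants risk hepatitis B reactivation if NA is stopped. It adds: "Although HBV reactivation can occur spontaneously, it can be triggered by immunosuppressive therapy", and lists withdrawal of antiviral drugs as a further trigger. Literal compliance with 8.3.6.2 could bring both triggers together in one participant. What is at stake is participant safety and consistent conduct across sites. No statistical quantity depends on it.

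**Working it through.** No arithmetic underlies the contradiction; it is checked by comparing the texts.

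**1. What the term covers.** The definition in Sections 1.1 and 2 includes NA, and Section 6.1 lists the three NAs among the study interventions. Section 10.10.1 itself uses the term in this wide sense: it discusses supplying and shipping oral study intervention, which can only be NA, and writes JNJ-3989/placebo when it means the injection.

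**2. The rules side by side.**

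| Source | Trigger | Product stopped | NA |
|---|---|---|---|
| 8.3.6.2 | Systemic steroids above 5 mg/day prednisolone equivalent needed for rash | Study intervention, permanently | Stopped, by definition |
| 10.10.1 | Prohibited medication used | Study intervention | Stopped, by definition |
| 7.1 | Disallowed drug required **and** no intention to stop it | JNJ-3989/placebo | Continued |
| 2.3.3 | None (general rule) | None | Continued to last visit |
| Appendix 5, Table 3, grade 3/4 rash | Grade 3 or 4 rash | JNJ-3989, permanently | Investigator may stop, consulting the sponsor |

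**3. Do the triggers overlap?** Systemic steroids above 5 mg/day are in Table 2, so the 8.3.6.2 trigger is a disallowed medication. That alone does not meet the 7.1 criterion, which also needs the second condition.

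- *Disallowed drug will not be stopped:* the 7.1 criterion is met. It keeps NA, while 8.3.6.2 and 10.10.1 stop it. Direct contradiction.
- *Disallowed drug will be stopped, such as a short steroid course:* this 7.1 criterion is not met, and its statement on NA is not engaged through it. The two sentences then contradict the general rule in 2.3.3.

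**4. A linked disagreement that affects the remedy.** Section 7.1 lists rash of grade 3 or higher among the cases in which NA is continued. Table 3 lets the investigator stop NA for the same rash. An amended 8.3.6.2 that cited both would point to two different rules.

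**5. How many participants could be affected?** Rates of steroid-treated rash or prohibited-medication use are not given, so no expected number can be stated. The Amendment 5 rationale gives a ceiling on those still in the study at that date: 17 Part 2 participants in the open-label phase, 2 in Part 2 follow-up, and at most all 22 from Part 1, who had finished JNJ-3989 (how many remained in follow-up is not stated). That is 17 + 2 + 22 = 41 at most, of whom only 17 could still be receiving JNJ-3989.

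**The case against.** The strongest reply is that no site would read the sentences this way. The protocol often uses the term narrowly when it discusses stopping. Section 7.1 is headed as discontinuation of study intervention yet covers only JNJ-3989/placebo, and its item on placebo participants who develop cirrhosis uses the bare term for not starting JNJ-3989. Section 8.3.6.1 does the same for ALT flares, where NA is expressly kept. The amendment history records a clarification, in Amendment 3, that NA goes on after early discontinuation of JNJ-3989. Section 8.3.6.2 refers rash monitoring to Table 3, whose grade 3 and 4 rows deal with JNJ-3989 and NA separately, so only steroid-treated rash of grade 1 or 2 lacks a product-specific row. Section 10.10.1 asks for sponsor discussion of any continuation issue. The immunosuppression examples in 2.3.1.2 are autoimmune disease, transplantation and immunocompromised states, not a steroid course for rash.

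Most of this stands, and it is why the practical risk is small. It shows that the wording is probably a slip; it does not make the wording consistent. The narrow usage is not uniform, least of all in 10.10.1, and where the protocol wants a JNJ-3989-only stop (7.1, 8.3.6.1, 8.3.6.5) it can say so.

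A reader might also infer that every steroid course for rash, or every use of a prohibited drug, contradicts Section 7.1. The documents do not support that: the 7.1 criterion requires that the participant does not intend to stop the drug.

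**Conclusion.** The inconsistency is real and minor. Two sentences, applied with the protocol's own definition, stop NA. They contradict Section 7.1 when the participant will not give up the disallowed drug, and the general NA-continuation rule in Section 2.3.3 otherwise. The conclusion rests on reading the defined term as defined.

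Two further inferences should be resisted. The protocol does not intend NA to be withdrawn in these situations; its general statements point the other way. Nor is there any evidence that a participant lost NA because of this wording. The Week 48 comparison is not put at risk from here on either, since the Amendment 5 rationale says that all participants are already past the double-blind phase.

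The two general safety sentences in 10.10.1, on stopping when a participant's safety is at risk, are not part of this point. They may properly reach NA when NA is the cause.

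**What to change.** 1. In the steroid sentence of 8.3.6.2 and the prohibited-medication sentence of 10.10.1, replace the general term with JNJ-3989/placebo and add that NA is continued.
2. Give the 10.10.1 sentence the same trigger as 7.1: the participant needs the disallowed drug and does not intend to stop it. Otherwise the two sections still differ on when to stop.
3. Reconcile 7.1 with Appendix 5 Table 3. For example, 7.1 could say that NA is continued, except that for grade 3/4 rash the investigator may stop it after consulting the sponsor, with a reference to Appendix 5. The amended 8.3.6.2 can then cite 7.1 safely. The same 7.1 item also covers allergic reactions, for which 8.3.6.3 gives the investigator the same discretion over NA, so one exception can serve both.

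The cost is a wording change in two sentences and one clause in 7.1. It adds no visit, procedure, data item or analysis.
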